6.4 Drug Treatment

According to concurrent guidelines and local routine treatment of subjects. All subjects recommended aspirin load dose (300 mg), clopidogrel load dose (300 mg) or teagro load dose (180 mg) before stent implantation, and recommended load dose for at least 6 hours prior to surgery. Perioperative anticoagulant therapy in all subjects included: general heparin or alternative anticoagulant (low molecular heparin, bivalirudine, enoxaparin) and ACT $>$ for 250 seconds during interventional surgery. After stenting, the subject lifelong aspirin for 75–150 mg per day. Biproxy antiplatelet therapy should last for at least 12 months, with the physician's determination that individual subjects may require clopidogrel / teagrelo treatment for life.

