Secondary endpoint	
The following indicators will be evaluated annually for 3 years.
 
• MACE(2-3 assessed annually)• Target lesion blood revascularization (TLR)• Target lesion failure (TLF)• Target vascular revascularization (TVR)• Target blood vessel failure (TVF)• Myocardial infarction (Q waves and non-Q waves)• Cardiac death• Noncardiac death• All-cause of death (cardiac and noncardiac)

	
 • In-stent thrombosis (ARC classification: determining / possible intrastent thrombosis)
Subsequent arrangements	Clinical follow-up for 30 days, 6 months, 12 months, 24 months, 36 months
Study duration	At 36 months, the
Antiplatelet therapy	Guidance according to current guide
Clinical inclusion criteria	
 • C1. Age > 18 • C2. STEMI Attack > 30 min, but < 12 h • ST segment elevation of at least 2 consecutive guided ≥ 1 mm or new LBBB on the C3. ECG • C4. is willing and able to provide informed consent form
Angiographic inclusion criteria	
The AI1. has at least one coronary artery associated with the infarction, in which the
 
 • Criminal lesion and suitable for stent placement • The reference diameter of criminal vessels is ≥ 2.5 mm but ≤ 4 mm • TIMI blood flow score ≤ 1 in the criminal lesion segment before guiding the lead to pass 
AI2. does not have excessive twists and calcification in criminal lesion segments that allow stents

Clinical Exclusion Standards	
Patients with CE1. have contraindications to the drugs to be used during the study
 
CE2. cardiogenic shock associated with hemodynamic instability
 
CE3. has bleeding or known coagulation disease
 
CE4. has a history of cerebrovascular accident (CVA) or transient ischemic attack (TIA) in the past 6 months, or intracranial tumor, aneurysm or arteriovenous malformation; or active peptic ulcer or active gastrointestinal (GI) bleeding in the past 2 months; or

	
scheduled major surgery within 6 weeks; or known platelet count <100,000 / mm³Or Hb <10g/dL
 
Planned CE5. surgery that cause deactivation of ADP receptor antagonist
 
Other serious CE6. diseases such as cancer may reduce life expectancy to below 1 year
 
CE7. recurrent myocardial infarction within 7 days after acute myocardial infarction

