5.1 Inclusion criteria

The 200 subjects who met the inclusion / exclusion criteria will undergo emergency angiography and the following

Clinical inclusion criteria

- C1. Age > 18
- C2. STEMI Attack > 30 min, but < 12 h
- ST segment elevation of at least 2 consecutive guided ≥ 1 mm or new LBBB on the C3. ECG

- C4. is willing and able to provide informed consent form

Angiographic inclusion criteria

The AI1. has at least one coronary artery associated with the infarction, in which the

- Criminal lesion and suitable for stent placement
- The reference diameter of criminal vessels is ≥ 2.5 mm but ≤ 4 mm
- TIMI blood flow score ≤ 1 in the criminal lesion segment before guiding the lead through

AI2. does not have excessive twists and calcification in criminal lesion segments that allow stents

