6.3 The Data Collection Plan

The following page is the observation and evaluation time during the study (Table 1)

Note:

1. The vital signs include: body temperature, pulse, breathing, and blood pressure.
2. Blood routine and biochemical activities include: white blood cells, red blood cells, platelet count, hemoglobin, liver function (ALT, AST), renal function (urea nitrogen, creatinine), blood lipid (total cholesterol, LDL cholesterol, high density lipoprotein cholesterol, triglyceride), blood sugar, etc.
3. Myocardial injury markers include: CK, CK-MB, TnT/TnI.

Table 1. Observation and Evaluation Schedule during the Study

Visit:	Visit: # 1			Visit 2:	Visit 3: 3	Visit 4: 4	Visit: 5	Visit 6: 6
Evaluation	Entering the Group	Random:	Discharg e:	30 Days \pm 7 Days	6 months \pm 30 Days	12 months \pm 30 Days	2 Year \pm 30 Days	3 years \pm 30 Days
Sign an informed consent form	✓							
Inclusion and exclusion criteria	✓							
Demographic Data	✓							
Related medical history and surgical history, coronary heart disease risk factors	✓							
vital signs, physical examination, weight, height	✓							
Myocardial injury markers	✓		✓					
12-Guided ECG	✓		✓					
Blood biochemistry and blood routine	✓		✓					

Aditant medication	✓		✓	✓	✓	✓	✓	✓
Coronary angiography	✓					✓		
Ststent implantation		✓						
Adverse events, serious Aevent end point related events	✓	✓	✓	✓	✓	✓	✓	✓
Postoperative antiplatelet therapy			✓	✓	✓	✓	✓	✓

Visit 1: entry (in hospital)

Written informed consent must be obtained only to determine the eligibility of the patient's participation in the study. The researchers should inform the subject that even if the subject agreed to attend the study and signed the informed consent form, cardiac catheterization may not warrant the study. The screening records are used to record information about candidates who do not meet the test selection criteria, including, but not limited to, the screening failure.

The subject was hospitalized for a planned coronary surgery (CAG or PCI). The selected CAG shall register and randomly as soon as possible to determine meeting the entry criteria and before any planned or emergency PCI.

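### Section 6.4 recommends antiplatelet loading at least 6 hours before the procedure for every subject, which does not fit a trial of emergency STEMI patients only; the interval should be deleted

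*Combined protocol and SAP*

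**What the plan says.** Section 6.4 (Drug Treatment) opens with a general rule: "According to concurrent guidelines and local routine treatment of subjects". The Antiplatelet therapy row of the Scheme Summary agrees: "Guidance according to current guide". Section 6.4 then becomes specific. For all subjects it recommends aspirin plus either clopidogrel or ticagrelor as a load before stenting, and adds a time interval: "recommended load dose for at least 6 hours prior to surgery". Surgery here means the study procedure; the next sentence sets the ACT target during interventional surgery.

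Section 5.1 defines who these subjects are:

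- Symptom window: "STEMI Attack > 30 min, but < 12 h".
- Culprit flow: "TIMI blood flow score ≤ 1 in the criminal lesion segment before guiding the lead through".
- Pathway: "The 200 subjects who met the inclusion / exclusion criteria will undergo emergency angiography".

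Section 6.3 (Visit 1: entry) is mixed. It says "The subject was hospitalized for a planned coronary surgery (CAG or PCI"), and then "The selected CAG shall register and randomly as soon as possible to determine meeting the entry criteria and before any planned or emergency PCI".

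**The concern.** A fixed wait of at least 6 hours between load and procedure presupposes a procedure that can be scheduled. The inclusion criteria describe the opposite: an acute infarct with little or no flow in the culprit artery, sent for emergency angiography. If a site acted on the sentence, it would postpone reperfusion in exactly those patients, which is a patient-safety matter. If a site ignored it, staff would have to decide, with an emergency patient waiting, whether they were departing from the protocol. Section 8.4 requires strict adherence and Section 9.1 requires departures to be documented.

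**Working it through.** The plan gives no figure to reproduce here, and Section 11.3 states that there is no sample size calculation. The check compares the sections and does simple arithmetic on the plan's own times.

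**Inputs**

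- Load-to-procedure interval: at least 6 h (Section 6.4).
- Onset window: more than 0.5 h and less than 12 h (Section 5.1).
- Planned subjects: 200, all for emergency angiography (Section 5.1).

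**Is there a subgroup the interval could fit?** Every subject must meet the STEMI window and the TIMI criterion. Section 6.3 requires catheterization to confirm angiographic eligibility, and randomization before PCI. The mention of planned procedures in Section 6.3 creates no elective stratum, because an elective patient would fail Section 5.1. The recommendation therefore covers 200 of 200 subjects and suits 0.

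**Is there an exception for emergency cases?** None is stated. Section 8.5, the only text on deviation in an emergency, concerns acute complications of the ultrasound examination.

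**What does literal compliance imply?** The minimum interval is 6 h × 60 = 360 min. The plan does not say which event ends the 12 h window, so both readings are shown.

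| Reading of the 12 h limit | Arithmetic | Consequence of following the advice |
|---|---|---|
| Onset to presentation or enrolment, with loading assumed to fall inside the window | 0.5 + 6 = 6.5 h; 12 + 6 = 18 h | Earliest procedure 6.5 to 18 h after onset, depending on when the load is given |
| Onset to PCI | 12 − 6 = 6 h | Load must be given within 6 h of onset; a patient loaded later cannot satisfy both rules |

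The documents give no distribution of loading times, so no average is computed. Neither reading is compatible with emergency angiography.

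**What if the guideline clause governs?** The fixed interval then drops out and the added delay is 0.

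**Does it touch the comparison?** The sentence addresses all subjects, so it is the same in the IVUS and angiography arms. By itself it introduces no difference between arms and changes no power or alpha figure.

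**The case against.** The strongest reply is that this is a minor clarification. The interval is only recommended, Section 6.4 and the Scheme Summary both defer to guidelines, and Section 6.3 asks for prompt randomization. The visit schedule in Table 1 contains no step for a 6-hour wait, and nothing in the documents shows that a site would apply one. The English is also visibly garbled elsewhere (the left aorta as a culprit site in Section 5.2, for example), so the sentence may be a translation error. Finally, the 18 h figure is the extreme of one reading of the 12 h window.

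Much of this stands. The delay is not mandated, it is zero where sites follow guidelines, and 18 h depends on the assumption stated with it. Calling the interval elective-style is also a clinical description that the plan does not use, though the argument does not need it.

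What the reply does not remove is the contradiction. The specific advice follows the general clause, is addressed to everyone, and nothing says which prevails. A translation error would be a reason to correct this text, not to leave it. The sentence serves no stated trial purpose, so nothing is lost by removing it.

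**Conclusion.** The concern holds and should be fixed. Section 6.4 contains advice that suits none of the 200 planned subjects. Taken literally, it puts at least 360 minutes between load and procedure in patients with little or no culprit flow. The onset-to-procedure range of 6.5 to 18 h assumes loading within the eligibility window. The plan sets no time limit on PCI itself, so the range describes delay and not a protocol violation. The matter is one of patient safety and internal consistency, not of bias or power. Confidence is medium, because the text is a rough translation and the source wording has not been seen.

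**What to change.** - Check the sentence in Section 6.4 against the source-language protocol.
- Delete the 6-hour interval. State instead that loading is given before stent implantation according to current guidelines and must not delay emergency PCI.
- In Section 6.3 (Visit 1: entry), replace the description of admission for a planned procedure with wording that matches the emergency pathway in Section 5.1.

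No dose or alternative timing is proposed here; the sponsor's clinicians should confirm the final wording. The cost is one sentence in Section 6.4 and one phrase in Section 6.3, with the ethics approval that Section 9.2 requires for a modified protocol. Sample size, visits and data collection do not change.

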6.5 Intravascular ultrasound examination

It is recommended that intraoperative intravascular ultrasound is recommended with a 40 MHz mechanical rotating probe for intravascular ultrasound.

Inoperative IVUS Guidelines

Standardized use of intravascular ultrasound is recommended:

It is recommended to use endovascular ultrasound preoperative, during and after surgery to guide PCI, with preoperative use of nitroglycerin to prevent spasm. After full exhaust, fully pass the lesion, automatically retract with

0.5mm/s speed and record the image to the vessel opening.

Refer to the ULTIMATE study results to optimize the PCI effect under IVUS guidance:

The IVUS standard standards shall meet the following 3 requirements:

The lumen area of the distal reference vessel with the stent segment MLA greater than 5.0 mm², or 90% after 1, ;

The patch load within the edge of 2, bracket is less than 50%;

3, has no edge mezzanine deep to mid level more than 3 mm

7. Data Management

The researchers must timely record the research data in accordance with the instructions provided in the CRF specified in the study programme.

7.1 Data Records

The investigator ensures the accuracy, completeness, and timeliness of the recorded data, and provides answers to the data queries. Trained researchers enter the data in the specified CRF data bar directory. Data will be frozen during audit, editing, and source data validation (SDV) to prevent further editing. The principal investigator signed the CRF and copies of the CRF will be archived at the Research Center.

All AE/SAEs s will be recorded in CRF and all subjects ' AEs/SAEs s occurring after the group are reported until the final visit period.

8. Ethics and Regulatory Requirements

8.1 Ethical considerations

The investigator will ensure that this study will follow the ethical principles outlined from the Helsinki Declaration of 1996; the National Ethics Review (trials) in 2007; and the 2002 international ethical guidelines for

biomedical research involving human subjects. It was conducted after obtaining the approval of the Ethics Committee of Zhongshan Hospital Affiliated to Fudan University.

8.2. Ethics Review

Copies of the test protocol, proposed informed consent, other written subjects information, and any suggested advertising materials must be submitted to IEC for written approval. A copy of the IEC written approval of the test protocol and the informed consent form must be obtained before recruiting subjects to enter the study and transport of research products.

Upon all subsequent revisions to the test protocol and all modifications to the informed consent form, the investigator must submit and obtain IEC approval if necessary. The investigator must notify local procedures of deviations or SAE, and intra-stent thrombosis, TVR, MI and death and other SAE reports obtained from the sponsor.

The investigator is responsible for obtaining annual approval and renewal of the TEC throughout the study period. Copies of the investigator report and the IEC renewal documents must be sent to the sponsor.

8.3 Informed consent form

Samples of informed consent will be provided to the investigator for use at the research center. The informed consent form used shall comply with the Good Clinical Code (GCP) guidelines of the International Coordination Conference (ICH), the ISO 14155, Helsinki Declaration, and current guidelines for applicable local regulations / laws.

Before attending the clinical trial, each subject must give written consent after the study content is fully explained to it in the easily understandable language of the subject. The subject must have the opportunity to raise

questions and to have satisfactory answers to them. Written informed consent must be properly recorded by signature and dated by the subject or his legal representative. If the subject is illiterate, an impartial witness may be required to sign on behalf of the patient. All subjects will receive a copy of the informed consent form. The consent process must be recorded in the subject's medical record.

8.4 Revision plan

This Programme must be strictly followed and can be changed only by written amendments. With appropriate approval, the revised test protocol will be distributed to all program recipients.

8.5 Scheme deviation under emergency conditions

Exit when endovascular ultrasound guided PCI due to acute complications from ultrasound.

9. Research Management

9.1 Programme Compliance

The study shall be conducted to the approved protocol and any breach or deviation shall be documented.

9.2 Scheme modification

After the protocol is approved by the Ethics Committee, if the clinical trial plan needs to be modified, the revised protocol shall be submitted to ethical approval, and if the group, the clinical trial can be continued after documents obtaining ethical approval.

10. Data management

10.1 Data collection and processing

Subject data will be collected over the Internet in a secure electronic data collection (EDC) system. The principal or associate investigator must ensure the accuracy and integrity of the recorded data and then provide electronic signatures on the corresponding eCRF.

10.2 Data quality assurance

Take the necessary control measures to ensure the accuracy and reliability of the data, including reviewing the clinical programs together with the clinical units, and making regular supervisory visits by the sponsor or other designated supervisors. During the clinical site supervision visit, review the accuracy and integrity of the case records and original data, and any errors will be preserved by the clinical unit or supervisor. Beyond this:

- Follow-up rate above 95%
- The Data Administrator challenges the data
- Important indicators for 100% verification
- Monitor 100% data of input system SDV.
- Review the data and give an audit report before the database is locked.

The case record table (Case Report Form, CRF) and the original research data are kept by the researchers, and the data management and statistical unit are responsible for the entry, cleaning, locking library and analysis report of the data.

10.3 Raw Data management

The investigator will retain all the necessary test documents and original data in the original form that support the data collected from the study subjects consistent with the ICH/GCP and SFDA GCP guidelines. Documents must be retained for at least 5 years after the completion of the clinical trial.

10.4 Deflection and system error control

All subjects who meet the inclusion / exclusion criteria and have signed an

informed consent form will be eligible for the trial. Continuous compliant subjects will be included in the study to minimize selection bias. Subjects were randomly assigned to each treatment group.

11. Statistical analysis

11.1 Statistical software

The research statistical analysis was done using SPSS (version 18.0 or later) and Stata (version 12.0 or later).

11.2 Statistical Methods

Statistical description is given below:

Continuous variables: number of group description examples, number of missing cases, average, median, standard difference, quartile range, minimum, and maximum.

Classification variable: Number of missing cases, number of splitting frequencies, and percentage of the group description.

Statistical tests: All statistical tests are bilateral tests, and P values less than or equal to 0.05 will be considered to be of statistical significance. (Unless specifically specified).

Overview of statistical methods: different analysis methods will be adopted according to the classification of groups and data characteristics, see the statistical analysis plan for details. The main statistical analysis methods include t test, card square test, Fisher accurate probability method, ANOVA, covariance, Logistic regression, CMH card square and rank and test methods to compare the differences among different groups.

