Contrast exclusion criteria	
The AE1. bifurcation lesion does not identify it as a criminal lesion
 
The AE2. criminal lesion is located in the left aorta
 
AE3. diffuse lesions associated with unidentifiable criminal lesions
 
AE4. or stent implantation due to stent thrombosis
 
AE5. may plan CABG bypass surgery within 30 days
 
AE6. patients develop renal failure during dialysis

Statistical Methods	
Major statistical assumptions	The IVUS guidance group may have better results than the angiography guidance, especially in TVR or TLR.
Statistical analysis	
Descriptive statistics (e. g., mean, standard deviation, n, minimum, maximum), or median (95% CI) (continuous variable), or frequency tables (classification variables), are used to summarize their demographic characteristics, clinical history, laboratory examination, and risk factors.
 
We will use Logistic regression to analyze the correlation of plaque morphology with clinical results both 12 and 36 months after STEMI.

Sample parameter size	To support the objectives, the sample size of this test will be at least 200 subjects.
Core Laboratory	Core Laboratory data Analysis

1. Research Background

Intravascular ultrasound (IVUS) has been increasingly used for selective and emergency percutaneous coronary intervention. Recent randomized controlled studies, large-scale registration studies, and meta-analysis have demonstrated significant advantages in reducing mortality, myocardial infarction, and target revascularization compared with separate angiographic-guided angiography.

As shown in previous studies [1-5], fewer clinical results on clinical studies of IVUS guided PCI in acute myocardial infarction (AMI) exist and the results remain controversial. This study will explore the effects of IVUS-guided PCI on clinical outcomes in patients with acute ST-segment elevation myocardial infarction (STEMI).

2. Research Objective

Comparing the long-term clinical efficacy of IVUS and angiography-guided PCI in dealing with acute STEMI.

3. study endpoint

.13. Main endpoint

The primary endpoint was major cardiac adverse events (MACE), defined as cardiac death at 12 months, recurrent myocardial infarction (MI, Q and non-Q waves), and target vascular revascularization (TVR).

.23. Secondary endpoint

The following indicators will be evaluated annually for 3 years.

- MACE(2-3 assessed annually)

- Target lesion blood revascularization (TLR)
- Target lesion failure (TLF)

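### Section 11.2 lets any P≤0.05 be called significant, and no hierarchy, multiplicity control or exploratory label covers the 29 implied secondary comparisons

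*Combined protocol and SAP*

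**What the plan says.** Section 11.2 sets a general default. It states that "All statistical tests are bilateral tests" and that "P values less than or equal to 0.05 will be considered to be of statistical significance". A qualifier follows in brackets, "Unless specifically specified", and the next paragraph defers the choice of methods with "see the statistical analysis plan for details". No exception is stated in the supplied text. Beyond section 11 and the Scheme Summary there is no further analysis-plan text.

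The endpoint sections name one primary endpoint: "The primary endpoint was major cardiac adverse events (MACE), defined as cardiac death at 12 months", together with recurrent MI and target vessel revascularization (TVR). Section 3.2 and the Scheme Summary then list ten secondary endpoints, introduced by "The following indicators will be evaluated annually for 3 years". MACE is on that list for years 2 and 3 only ("MACE(2-3 assessed annually").

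The one stated hypothesis is in the Scheme Summary, in the row for major statistical assumptions: "The IVUS guidance group may have better results than the angiography guidance, especially in TVR or TLR". The Scheme Summary also plans logistic regressions of clinical results on plaque morphology at 12 and 36 months. Section 11.3 calls the study a pilot without a sample size calculation.

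**The concern.** The significance rule does not separate the one primary comparison from the many secondary ones. As written, a secondary endpoint that crosses 0.05 at any annual assessment may be reported as significant in the same terms as the primary, even when 12-month MACE shows no difference. The 5% error rate that a reader attaches to the word significant does not apply to a result picked from a large set.

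The hypothesis adds to this. It emphasises TVR, which is both a component of MACE and a secondary endpoint, and TLR, which is secondary only. It does not mention 12-month MACE, so nothing in the hypothesis ties a claim of benefit to the declared primary endpoint.

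**Working it through.** The documents state no familywise error rate, power or event rates, so there is no figure to reproduce. The check counts the comparisons and estimates the false-positive rate when IVUS has no effect.

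**Count.** The ten listed secondaries are MACE, TLR, TLF, TVR, TVF, MI, cardiac death, noncardiac death, all-cause death and stent thrombosis. Nine have three annual assessments and MACE has two: 9 × 3 + 2 = 29. With the primary there are 30. This assumes a between-arm comparison at each assessment.

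**Inputs from the documents.** 200 subjects at 1:1, so about 100 per arm (Scheme Summary, section 4); two-sided P≤0.05 (section 11.2); chi-square and Fisher exact tests are both listed, and neither is assigned to an endpoint (section 11.2).

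**Assumed inputs.** In the base case the yearly probabilities, for year 1 and then for each of years 2 and 3, are:
- cardiac death 2%, 1%
- noncardiac death 1%, 1%
- stent thrombosis 1%, 0.5%
- target-vessel MI 2%, 1%
- other MI 1%, 1%
- TLR 3%, 2%
- other TVR 1.5%, 1.5%

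All rates are multiplied by 0.5, 1, 2 or 3 to cover a range. Stent thrombosis leads to target-vessel MI and to TLR with probability 0.8 each, and target-vessel MI leads to TLR with probability 0.4. Events after death are not counted. TLF and TVF, which the documents do not define, are taken as cardiac death, target-vessel MI, and TLR or TVR respectively. Endpoints are cumulative at years 1, 2 and 3, and both arms have the same rates.

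**Result.** There were 8,000 simulated trials per row. Entries are the percentage of null trials with at least one P≤0.05 among the 30 comparisons:

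| Assumed 12-month MACE | Chi-square, either direction | Chi-square, favouring IVUS | Fisher, either direction | Fisher, favouring IVUS |
|---|---|---|---|---|
| 5% | 36.4 | 19.1 | 15.0 | 7.7 |
| 10% | 44.0 | 24.0 | 22.5 | 11.9 |
| 19% | 48.0 | 27.1 | 30.1 | 15.9 |
| 28% | 49.8 | 27.1 | 34.1 | 17.9 |

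The Monte Carlo standard error is at most √(0.5 × 0.5 / 8,000) = 0.6 percentage points. The table includes the primary. Leaving it out, so that only the 29 secondaries count, lowers every entry by less than half a percentage point.

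**Primary alone.** 12-month MACE reaches P≤0.05 in 4.4% to 5.4% of null trials by chi-square and 2.3% to 3.4% by Fisher.

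**TVR or TLR alone, at any of the three years.** 13% to 15% by chi-square (7% to 8% favouring IVUS); 6% to 10% by Fisher (3% to 5%).

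**Second set of assumed rates.** With 12-month MACE of 12.4% and 23.6%, chi-square and 20,000 trials each, at least one secondary reaches P≤0.05 in 42.6% and 46.6% of null trials. Among trials where the primary is not significant, the figures are 39.4% and 43.8%.

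**The case against.** There is a fair case that the plan is in better order than this suggests. It names one primary endpoint at one time point and lists the secondaries separately, which is itself a hierarchy of endpoints. Section 3.2 says that the secondaries are evaluated yearly, not that each is tested between arms each year, so the 29 comparisons are an inference. Section 11.2 allows exceptions and refers to an analysis plan that may settle the matter. Sparse endpoints such as stent thrombosis and death would normally go to Fisher's test, where the rates are lowest.

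These points narrow the finding. Naming a primary endpoint protects that test, but it does not say how a secondary P value may be described, and the rule in section 11.2 answers that in the wrong way. No exception appears in the supplied text, so the finding is limited to that text. Even the lowest Fisher figure, 15%, is three times 5%.

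Three stronger readings are tempting, and the documents do not support them:
- A reader might compound 5% over 29 independent tests and infer that a false positive claim for IVUS is more likely than not. The endpoints are nested (TLR within TVR; cardiac death, MI and TVR within MACE; cardiac within all-cause death) and the yearly assessments are cumulative. With that overlap, no assumed scenario exceeds 50% in either direction or about 27% favouring IVUS.
- A reader might take TVR or TLR as an either-or success criterion. The sentence states a general expectation with an emphasis. Even as a criterion, two tests at one time point give at most 5% + 5% = 10%, or 5% favouring IVUS.
- A reader might infer that the primary error rate is inflated, or that the publication will lead with a secondary result. The first is untrue on the figures above; the second is a guess about conduct.

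**Conclusion.** The concern holds in a limited form. The primary comparison of 12-month MACE is sound as to type I error, at about 5% or below. For everything else, the supplied text gives the word significant to any P≤0.05 and has no hierarchy, adjustment or exploratory label. The chance of at least one false significant secondary result is roughly 15% to 50% in either direction, against 5% for a single test, and 8% to 27% favouring IVUS, against 2.5% for a single test in that direction.

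These ranges rest on assumed event rates, an assumed overlap of endpoints, 100 per arm, and a between-arm comparison at each assessment. The choice of test alone moves the figure by a wide margin: at 10% MACE it is 44.0% by chi-square and 22.5% by Fisher. That section 11.2 leaves the test open is therefore part of the uncertainty. The size is uncertain; that it is several times the nominal rate is not, in any scenario examined. The plan should be changed, but the defect does not undermine the primary analysis.

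**What to change.** Before outcomes by arm are seen, add to section 11.2:

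> The between-arm comparison of 12-month MACE is the only confirmatory test, at two-sided 0.05. Secondary endpoints, all 2- and 3-year assessments and the plaque-morphology logistic regressions are exploratory: they are reported as estimates with 95% CIs, and any P value is nominal and not described as significant.

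Reword the hypothesis in the Scheme Summary so that 12-month MACE is the hypothesis tested and TVR and TLR are supportive. If a separate analysis plan already contains such a rule, section 11.2 should state it or point to it explicitly.

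No alpha adjustment is involved, and the primary test loses no power. The edit is wording only, but its consequence is real: the sponsor gives up formal significance claims on secondary endpoints and on all 2- and 3-year results, although the stated objective is long-term efficacy. For a study that calls itself a pilot and has no sample size calculation, that is a reasonable price. If the sponsor wants a formal claim on a later or secondary endpoint, the alternative is a pre-specified testing hierarchy, also fixed before outcomes by arm are seen.
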